# Lead Electrocardiogram Report

ECG Performed	$\Box$ YES $\Box$ NO	
DATE	//	
	(dd/mm/yyyy)	
	Abnormal Q-waves	$\Box$ YES $\Box$ NO
	Abnormal ST segment changes	$\Box$ YES $\Box$ NO
	Abnormal T wave inversion	□ YES □ NO

Site ID	Subject Number	Birth Year

# Medical History Form

Note: Peripheral Vascular History is collected on a separate form.

- 1. Has the subject ever smoked?  $\Box$  YES  $\Box$  NO
- 2. Does the subject currently smoke?  $\Box$  YES  $\Box$  NO

	Check if History	Check if No History	Diagnosis or Abnormality
1.			Peripheral Vascular Disease
2.			Hypertension
3.			Hyperlipidemia
4.			Angina Pectoris
5.			Previous Percutaneous or Surgical Coronary Revascularization (If History When:)
6.			Congestive Heart Failure
7.			Renal Insufficiency
8.			Liver Disease
9.			Cerebrovascular disease (known carotid artery disease, history of minor or major stroke or transient ischemic attack)
10.			Chronic Obstructive Pulmonary Disease (COPD)
11.			Obesity
12.			Deep Vein Thrombosis

Site ID ____ Subject Number ___ Birth Year ____

Medical History (Continued)

13. Previous Q wave or non-Q wave MI?						
13.1. Most recent MI date:/ (dd/mmm/yyyy)						
14. History of prior percutaneous coronary revascularization?	$\Box$ Yes $\Box$ No $\Box$ Unknown					
14.1. Was the target vessel revascularized?	$\Box$ Yes $\Box$ No $\Box$ Unknown					
14.1.1. Method of revascularization	n: $\Box$ PTCA $\Box$ Stenting					
15. History of prior CABG?	🗆 Yes 🗆 No					
16. Diabetes mellitus?	$\Box$ Yes $\Box$ No $\Box$ Unknown					
4.1. Most recent pre-hospital treatment: 🗆 Insulin 🗆 Oral antidiabetic agents 🗆 Diet						
17. Is there premature CAD in a first-degree relative? $\Box$ Yes $\Box$ No $\Box$ Unknown						
18. Number of diseased major coronary arteries that have received catheter treatment:						
	$\Box 0 \Box 1 \Box 2 \Box 3$					
Assessment of Anginal Status						
19. $\Box$ Stable angina $\Box$ Unstable angina $\Box$ MI						
20. Worst Canadian Cardiovascular Society Class leading to this revascularization:						
$\Box$ CCS 0 $\Box$ CCS1 $\Box$ CCS2 $\Box$ CCS3 $\Box$ CCS 4 $\Box$ UNK						
21. Did the patient have a positive stress test? $\Box$ YES $\Box$ NO $\Box$ UNK						

# CVT ISR Trial FIH Trial Protocol Number: TP1125 Case Report Forms

Г

Site ID		Subject Number Birth Year						
Pre-Procedure Laboratory Blood Values								
1. Is the subject female and of childbearing potential? $\Box$ YES $\Box$ NO $\Box$ NA (if N								
	1.1.	If yes, sample date of pregnancy test:						
	1.2.	Result of pregnancy test: $\Box$ Postive $\Box$ Negative $\Box$ Not Done						

Blood Test Sample Date:	
DD MM YYYY	

_			Range		Clinically Significant		Comment	
Parameter	Result	Unit	IN	O High	UT Low	(if out o Yes	of range) No	or Not Done
WBC								□ Not Done
Differential WBC								
Eosinophils								□ Not Done
Basophils								□ Not Done
Neutrophils								□ Not Done
Monocytes								□ Not Done
Lymphocytes								□ Not Done
Hemoglobin								□ Not Done
Hematocrit								□ Not Done
Absolute Platelet Count								□ Not Done
Serum Creatinine								□ Not Done
Prothrombin Time								□ Not Done
Activated Prothrombin Time								□ Not Done
Site ID	Subject Number	Birth Year						
---------	----------------	------------						
---------	----------------	------------						

CK and/or CK-MB cardiac Troponin

 $\hfill\square$  Not done.

Cardiac Enzymes	Date of Test: (dd/mm/yyyy)	Time (24 hour clock)	Value (U/L)	Upper Normal Limit (U/L)
СК	//	:		
CK-MB	//	:		
Troponin	//	:		

Site	e ID Subjec	t Number	Birth Year
	Antiplatelet and A	Anticoagulant Me	dication
1. 2.	Was Aspirin Administered Was an Antiplatelet Administered	□ YES □ □ YES □	NO NO
3.	What anticoagulant was administered	:	
4.	Was a glycoprotein (GP) IIb/IIIa recep	ptor blocker used: 🗆 Y	YES $\Box$ NO

Site ID	Subject Number	Birth Year
Target Lesion Treatment D	Procedural Form CB # 1 □ DCB # 2 □	

 
What was the location         
 
□ Femoral □ F
 
 
 
Arterial sheath size □
 
	of vascular access Radial □ Brachial 5F □ 6F □ 7F □ 8F	

 
3. ISR Stent Location
 
Right Coronary Artery
 
Proximal      Mid      Distal
 
Right Post. Descending
 
	
 
□ Left Anterior Descending
 
□ Proximal □ Mid □ Distal
 
□ Diagonal branch
 
	
 
□ Circumflex.
 
□ Proximal □ Mid □ Distal
 
□ Obtuse Marginal
 

4. Type of stent with ISR	$: \square BMS \square DES Sirolimus \square DES$	Everolimus 🗆 DES Paclitaxel
	□ DES Zotarolimus □ DES other	drug Specify

 
Angiographic Assessm
 
Reference Vess
 
Minimum Lum
 
Lesion Length
 
% Diameter ste
 
	ent 🗆 Visual 🗆 QCA sel Diametermm inal Diameter in Lesionmm mm enosismm	
6. CVT DCB Lot #	and serial number	(if applicable)
7. CVT DCB Size:		
8. Maximum pressure uso	ed with:	(atm)
9. a. Time device entered	d the vasculature (HH:MM):	:
b. Time the device wa	s inflated (HH:MM):	:
c. Was the balloon inf	lated against the vessel wall for 1 mi	nute or more? $\Box$ YES $\Box$ NO
d. Duration the balloo	n was inflated (minutes: seconds)	:
10. Percent stenosis after t	he CVT DCB Deployment:	0⁄0
11. Dissection after this cat	heter treatment (Grade): $\Box$ 0/Not A $\Box$ D $\Box$	Applicable 🗆 A 🗆 B 🗆 C E 🗆 F

Site	ID     Subject Number     Birth Year
	Procedural Form (Continued)
12. ]	$\begin{tabular}{lllllllllllllllllllllllllllllllllll$
	13.1. If yes specify device used
	13.2. If stent used, what type of stent $\Box$ BMS $\Box$ DES Specify
13.	Was the target lesion post-dilated following the use of DCB # 1? □ YES □ If NO, go to question 2.
	13.1. If yes:
	Balloon diameter :mm
	Balloon length :mm
	13.2. Maximum pressure used: (atm)
	13.3. Percent stenosis after post-dilatation (visual estimate):%
	13.4. Dissection after post-dilatation (grade): $\Box$ 0/Not Applicable $\Box$ A $\Box$ B
	$\Box \ \mathbf{C}  \Box \ \mathbf{D}  \Box \ \mathbf{E}  \Box \ \mathbf{F}$
14.	Treatment required to treat dissection: $\Box$ YES $\Box$ NO $\Box$ N/A
	14.1. If yes specify device used
	14.2. If stent used, what type of stent $\Box$ BMS $\Box$ DES Specify
15.	Indicate the final percent stenosis of target lesion after all treatment (pre-dilatation, treatment catheter, post-dilatation and, if applicable, stenting):%

# Procedural Form (Continued)

 $\Box$  Check if the subject had a second balloon used and complete a second procedural form.

Post-Index Procedure Angiography

16.Was an angiogram of the study lesion captured during the procedure per angiographic core lab instructions ?  $\Box$  YES  $\Box$  NO

a. If yes, was the angiogram sent or uploaded to the core lab?  $\Box$  YES  $\Box$  NO

-

#### **Blood Assessment**

1.	Were blood labs taken post-procedure and pre-discharge? $\Box$ YES	$\square$ NO
	If yes, complete the Laboratory Blood Values Form.	

#### CK and/or CK-MB cardiac Troponin

Cardiac	Date of Test:	Time	Value	Upper Normal
Enzymes	(dd/mm/yyyy)	(24 hour clock)	(U/L)	Limit (U/L)
СК	//	:		
CK-MB	//	:		
Troponin	//	:		

### 12-Lead Electrocardiogram Report

ECG Performed	$\Box$ YES $\Box$ NO	
DATE	//	
	(dd/mm/yyyy)	
	Abnormal Q-waves	$\Box$ YES $\Box$ NO
	Abnormal ST segment changes	$\Box$ YES $\Box$ NO
	Abnormal T wave inversion	$\Box$ YES $\Box$ NO

**Reminder:** Record all medications including study medications on the **Concomitant Medications Log**. Record all adverse events unresolved as of the end of the index procedure through discharge on the **Adverse Events Log**.

edications	1 month follow un	- 6 Month fallo	V 110
$\square 12 \text{ Month follow}$	w up $\Box$ 24 Month fo	llow up $\Box$ 36 Mo	nth follow up
Aedications	Pre-Procedure	During Procedure	Post-Procedure
ASA	□ YES		□ YES
	□ NO		□ NO
	🗖 UNK		🗖 UNK
Clopidogrel	□ YES	□ YES	□ YES
1 0	□ NO	□ NO	□ NO
	□ UNK	□ UNK	□ UNK
Ticlopidine	□ YES	□ YES	□ YES
	□ NO	□ NO	□ NO
	□ UNK	□ UNK	UNK
Other Anti coagulants	□ YES	□ YES	□ YES
C	□ NO	□ NO	□ NO
	UNK	UNK	UNK
IIb/IIIa Inhibitors			

Sit	e ID Birth Year Birth Year
	1 Month Follow-up Visit
Dat	te of Subject Visit:
	Check if the visit was not performed
Ge	neral Assessment
1.	Did the subject visit the clinic?
	

☐ If NO, was the visit conducted via telephone?

	$\Box$ YES
2.	Were current medications discussed?
	□ If YES, update the Concomitant Medications Log as appropriate
	$\Box$ NO
3.	Was the subject asked if any adverse events occurred from the last study visit
	□ If YES, update the Adverse Event Log as appropriate
	$\square$ NO
4.	Did the subject have any coronary reinterventions since the last study visit?
	□ If YES, complete the Intervention/Revascularization Form and record the precluding adverse event on the Adverse Event Log
	$\square$ NO

ECG Performed	$\Box$ YES $\Box$ NO $\Box$ NA	
DATE	//	
	(dd/mm/yyyy)	
	Abnormal Q-waves	$\Box$ YES $\Box$ NO
	Abnormal ST segment changes	$\Box$ YES $\Box$ NO
	Abnormal T wave inversion	$\Box$ YES $\Box$ NO

Site	Birth Year Birth Year			
	6 Month Follow-up visit			
Date	Date of Subject Visit: $ -                                   $			
Clinical Follow up				
1.	Were current medications discussed?			
	□ If YES, update the Concomitant Medications Log as appropriate			
2.	Was the subject asked if any adverse events occurred from the last study visit?			
	□ If YES, update the Adverse Event Log as appropriate			
	$\square$ NO			
3.	Did the subject have any reinterventions since the last study visit?			
	□ If YES, complete the Intervention/Revascularization Form and record the precluding adverse event on the Adverse Event Log			
	$\square$ NO			

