3.4 Other Clinical Endpoints

³ Garcia-Garcia HM, McFadden EP, Farb A, et al. Standardized End Point Definitions for Coronary Intervention Trials: The Academic Research Consortium-2 Consensus Document. Circulation. 2018;137(24):2635-2650. doi:10.1161/CIRCULATIONAHA.117.029289

⁴ Moussa ID, Klein LW, Shah B, et al. Consideration of a new definition of clinically relevant myocardial infarction after coronary revascularization: an expert consensus document from the Society for Cardiovascular Angiography and Interventions (SCAI). J Am Coll Cardiol. 2013;62(17):1563-1570. doi:10.1016/j.jacc.2013.08.720

- Target lesion failure (TLF) at 30 days, 1, 2 and 3 years, post-procedure, defined as a composite rate of cardiovascular death, target vessel myocardial infarction and clinically-driven target lesion revascularization (TLR).
- Target vessel failure (TVF) at 30 days, 180 days and 1, 2 and 3 years post-procedure, defined as a composite rate of cardiovascular death, target vessel myocardial infarction, and target vessel revascularization (TVR).
- Clinically-driven target lesion revascularization (TLR) at 1, 2 and 3 years post-procedure.
- Clinically-driven target vessel revascularization (TVR) at 180 days and 1, 2 and 3 years post-procedure.
- Rate of vascular access site complication, defined as the combined rate of hematoma, AV fistula or a pseudoaneurysm that required intervention, such as surgical repair or transfusion, prolonged hospital stay or required a new hospital admission.
- Lesion success (per device), defined as achievement of a final in-lesion residual diameter stenosis of <30% (by QCA), using any device after wire passage through the lesion. Pre- and post-dilatation of the lesion with a non-study device is considered part of assigned device treatment.
- Technical success (per device), defined as achievement of a final in-lesion residual diameter stenosis of <30% (by QCA), using the CVT Everolimus-coated PTCA Catheter without a device malfunction after wire passage through the lesion. Pre- and post-dilatation are considered part of assigned device treatment.
- Clinical success (per subject) defined as technical success without the occurrence of major adverse events during the procedure.
- Procedural success (per subject) defined as lesion success without the occurrence of major adverse events during the procedure.

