5. ADVERSE EVENTS

5.1 Adverse Events

At each evaluation, the investigator will determine whether any adverse events (AEs) have occurred. For the purpose of this protocol, an adverse event is any untoward medical occurrence, unintended disease or injury, or untoward clinical signs (including laboratory findings) in subjects, users or other person, whether or not related to the investigational medical device.

In this study, subjects should be encouraged to report AEs spontaneously or in response to general, non-directed questioning. If it is determined that an AE has occurred, the investigator should obtain all the information required to complete the AE Form of the CRF.

In addition, subjects will be instructed to contact the investigator, and/or study coordinator if any significant adverse events (e.g., MACE) occur between study evaluation visits.

AE collection will start when CVT Everolimus-coated PTCA Catheter has entered the vasculature.

Adverse events should be followed to resolution or stabilization, and if an ongoing AE changes in severity, a new AE entry for this event should be recorded. If a mild adverse event changes to a moderate or severe adverse event, the end date for the mild event and the start date for the moderate or severe event should be the same. Additionally, the mild event is considered resolved with the initiation of the moderate or severe event.

Adverse events that are present at the end of a subject's participation in the study should be marked as on-going on the case report form and the subject should receive posttreatment follow-up as appropriate.

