# **Investigators Responsibilities**

- 1. Have and maintain the resources necessary to conduct the clinical investigation properly.
- 2. Ensure that conducting the clinical investigation is not nor will not cause a conflict of interest.
- 3. Obtain from the sponsor information which the clinical investigator judges essential about the device and be familiar with this information.
- 4. Understanding of the Clinical Investigational Plan (CIP)/Protocol prior to signing it.
- 5. Compliance with the CIP and any amendments.
- 6. Support the monitor in their activities to verify compliance with the CIP, to perform source data verification, and to correct case report forms where inconsistencies or missing data is identified.
- 7. Discuss with the sponsor and monitor any question of modification of the clinical investigation plan and obtain written approval of the sponsor.
- 8. Ensure the clinical investigation plan is followed by all persons responsible for the conduct of the clinical investigation at the institution. Any deviation must be documented and reported to the sponsor.
- 9. Make the necessary arrangements to ensure the proper conduct and completion of the clinical investigation.
- 10. Make the necessary arrangements for emergency treatment, as needed, to protect the health and welfare of the subject.
- 11. Ensure that appropriate ethics committee approval has been received prior to the start of the clinical investigation at the center.
- 12. Provide the results from the ethics committee to the sponsor.
- 13. Inform the ethics committee and request opinion and/or approval for any significant change in the clinical investigation plan that has been approved by the sponsor.
- 14. Inform the ethics committee about any serious adverse device effect and/or serious adverse event.
- 15. Inform the sponsor about all adverse events, serious adverse ecents and adverse device effects in a timely manner.
- 16. Attempt to ensure an adequate recruitment of subjects.
- 17. Ensure that the subject has adequate information to give informed consent.
- 18. Ensure that informed consent is obtained and documented.

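### The pre-discharge CRF reminder is narrower than the protocol's adverse event rule, so events that start and resolve during the procedure risk being left off the Adverse Event Log

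*Combined protocol and SAP*

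**What the plan says.** **Protocol rule.** Section 5.1 states: "AE collection will start when CVT Everolimus-coated PTCA Catheter has entered the vasculature". Footnote 4 to Table 3 and to Appendix F repeats this, and both schedules mark adverse events in the Procedure column. Section 5.1 adds that once an event is found to have occurred, "the investigator should obtain all the information required to complete the AE Form of the CRF". None of these places makes collection depend on whether the event has resolved.

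**CRF reminder.** In Appendix L, the page with post-procedure bloods, cardiac enzymes and ECG closes with: "Record all adverse events unresolved as of the end of the index procedure through discharge on the" Adverse Events Log.

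**Next prompt.** Item 3 of the 1-month form reads: "Was the subject asked if any adverse events occurred from the last study visit".

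**Other relevant records.** The Adverse Event Log has a timing field with an *Intra-Op* option. The Procedural Form records dissection grade after the study balloon and after post-dilatation, and has an item headed "Treatment required to treat dissection". Appendix H gives investigators a general duty: "Inform the sponsor about all adverse events", along with serious events and device effects.

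**The concern.** The reminder and the protocol define different sets of events. An event that starts with the study balloon in place and settles before the last catheter is removed falls inside the Section 5.1 rule but outside the literal reminder. Coronary spasm, a brief arrhythmia and an acute reaction to contrast are examples, and Section 5.2 anticipates all three.

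Sites tend to complete a CRF from its page-level instructions, so the narrower wording may prevail in practice. These events are the closest in time to device exposure. Section 9.6 describes the trial as first-in-human, and with 50 subjects a few missing entries could change the description of acute tolerability. An event left off the log also gets no investigator rating of severity (Section 5.3) or device relationship (Section 5.4).

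**Working it through.** The plan states no figure on this point and no calculation applies. The check sets the instructions side by side.

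1. **Window.** Section 5.1 and footnote 4 of both schedules open collection at catheter entry. The reminder covers events still unresolved at the end of the procedure, through discharge. The difference between the two is the set of events with both onset and resolution between catheter entry and the end of the procedure.

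2. **Does another CRF prompt cover that set?**
   - *Procedural Form:* no adverse event prompt is visible. It has dissection fields (grade, treatment needed, device and stent type). It has no visible field for spasm, arrhythmia, perforation, abrupt closure or allergic reaction, although Section 5.2 or Appendix B lists or defines these.
   - *Adverse Event Log:* the *Intra-Op* option shows that the log can hold such events. It does not tell sites to enter resolved ones, since an event that began in the procedure and continued afterwards would carry the same mark.
   - *1-month form:* looks back only to the last study visit, and the question goes to the subject.
   - *Study completion form:* asks whether events were reported during the study and has the log brought up to date. It does not ask whether an event went unlogged.
   - *Serious Adverse Event Notification Form:* covers serious events, which the reporting table in Section 9.8 requires within 24 hours. Non-serious events are outside it.

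   The visible forms therefore do not expressly request the set in step 1.

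3. **What is recorded for dissection?** Grade and treatment, whether or not it resolved. Severity, seriousness and relationship to device or procedure are fields of the Adverse Event Log, not of the Procedural Form.

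4. **Which outcomes could be affected?** The synopsis scores clinical and procedural success by absence of major adverse cardiac events during the procedure. Appendix B defines these as death, myocardial infarction, emergent bypass surgery or clinically driven repeat target lesion revascularization. Death and bypass surgery do not resolve unrecorded on the table. Periprocedural infarction is judged from enzymes and ECG, collected on the same CRF page as the reminder. Revascularization has its own form. The reminder is not shown to remove any component, and the same reasoning covers target lesion failure. What remains exposed is the non-serious adverse event listing.

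**The case against.** The strongest reply is that the protocol governs and already requires these events. Section 5.1 is explicit, the log has an intra-operative option, and Appendix H requires all adverse events to reach the sponsor. Section 9.8 has event details retrieved at monitoring visits, and Appendix H provides for source data verification. The reminder sits on a page covering the end of the procedure to discharge, so it can be read as asking which events carried over into that window. The CRF appendix also warns that its version may not be current: FRM1123 Rev. 01 is effective 09-Jun-2021, before protocol Revision A of 22-Sep-2021.

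Much of this stands, and it rules out two stronger readings:

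- A reader might infer that sites are told to log *only* unresolved events. That word is not in the reminder, and nothing there expressly excludes resolved events.
- A reader might infer that resolved intra-procedural events are lost to the safety data. The documents do not support this, because the Section 5.1 duty remains, dissections are recorded elsewhere, and serious events have their own form.

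The reply does not remove the conflict. The general duties do not correct a page-level instruction that is narrower than the rule, and no visible prompt asks for the missing set. Monitoring could recover such events only where the source notes mention them and the monitor looks.

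**Conclusion.** The inconsistency is real and worth correcting. Followed literally, the reminder puts transient intra-procedural events other than dissection at risk of being left off the Adverse Event Log. Dissections are recorded elsewhere, but without severity or relatedness. The direction of bias is downward, in the non-serious device adverse event profile. This assumes that some sites follow the form rather than Section 5.1, and that the live CRF carries the same wording.

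The size cannot be estimated. A reader might assume that 5–15% of procedures have a transient event, giving 0.05 × 50 = 2.5 to 0.15 × 50 = 7.5 subjects. The documents supply no such rate, and the count would further require every site to follow the reminder and log none of these events. The nearest figure, in Appendix J, is above 1% and below 10% for dissection with ischemia or infarction (0.01 × 50 = 0.5 to 0.10 × 50 = 5 subjects). That describes a different event, for which the Procedural Form has dissection fields.

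A reader might also infer inflated success rates, at 1/50 = 2 percentage points per missed event, because Section 3.4 uses looser wording than the synopsis: "Clinical success (per subject) defined as technical success without the occurrence of major adverse events during the procedure". That section leaves the term undefined. Under the synopsis wording and the Appendix B definition, no qualifying event is shown to be lost. No effect on the primary safety endpoint is shown either.

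**What to change.** 1. Check the reminder's wording in the current revision of FRM1123. If it is unchanged, continue as follows.
2. Replace it with: *Record on the Adverse Events Log all adverse events from the time the CVT catheter entered the vasculature through discharge, whether or not they had resolved by the end of the procedure.*
3. Put the same prompt on the Procedural Form, where these events are first seen.
4. For subjects already treated, check procedure notes at routine monitoring for resolved intra-procedural events and add any that are missing.

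The cost is one sentence on two CRF pages, a short site memo and a few more log lines. No endpoint, sample size or analysis changes.
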